8.1.3 Selection of measurements for endpoints

For the primary endpoint, the SADE-free rate will be assessed by collecting and evaluating adverse events until the 3-month follow-up (see section 7.2.1).

For **secondary endpoint 1**, the R-wave is measured via the programmer. Due to its automatic measurement, this figure unambiguously indicates the device's ability to detect the patient's heart beats. The noise burden for **secondary endpoint 2** is continuously recorded by the device. The value retrieved from the device with the help of the programmer clearly measures the time during which the device is unable to detect the patient's heartbeats.

P-waves are not detected by the device; therefore, the investigators decide whether P-waves are visible in a test ECG. A periodic sECG was chosen as the sample ECG because during arrhythmia, P-waves are often not present. The P-wave visibility (**secondary endpoint 3**) is determined by counting P-waves and QRS-complexes.

For the **secondary endpoint 4** the long-term safety of the BIOMONITOR III system, all SADEs related to the BIOMONITOR III system are collected by the investigators and evaluated by an internal adjudication board as described above. An observation period of 12 months was chosen to significantly extent the monitoring period for safety events beyond the 3 months which are defined for the primary endpoint.

8.1.4 Methods

8.1.4.1 eCRFs

During the course of the study, all clinical procedures are performed according to clinical routine. All parameters and measurements that are recorded within the study are described in this section and are documented on the following electronic Case Report Forms (eCRFs). The corresponding time schedule is described in section 9.1:

- Enrollment
- Baseline
- Medical History
- Insertion

- 1st follow-up
- 3-month follow-up
- 12-month follow-up
- Adverse Event
- Device Deficiency
- Device Log
- Explantation/Deactivation
- Concomitant Medication Log
- Deviation Log (site)
- Device Accountability Details (for Australia only)
- Termination

Source data, e.g. medical records, have to be available for all data entered in the eCRFs, unless specified differently by this CIP (compare sections below). eCRFs will be verified by the sponsor's clinical monitors.

If necessary, the sponsor will request pseudonymized electronic source documents (e.g. exported programmer files or medical records about AEs for the assessment of seriousness and relatedness).

Patients have to consent to the use of their medical data prior to enrollment by signing the informed consent form (ICF).

8.1.4.2 Source data verification of enrollment criteria

For the following inclusion/exclusion criteria, the eCRF is accepted as source:

- Patient is able to understand the nature of the study and to provide written informed consent.
- Patient is willing and able to perform all follow-up visits at the investigational site.
- Patient is pregnant or breast feeding.
- Patient is participating in another interventional clinical investigation.
- Patient's life-expectancy is less than 12 months.

The following Source data sheets (SDS) are recommended to be used:

- Insertion SDS
- 1st follow-up, 3-month and 12-month follow-up SDS
- Explantation / Deactivation SDS

8.1.5 Equipment to be used for the assessment of variables

The following equipment is used during the study to collect data in combination with the BIOMONITOR III or as accessory:

• External programming device:	BIOTRONIK Renamic (or successors) BIOTRONIK ICS3000 (or successors)
• BIOTRONIK programmer software:	Programmer software PSW1901.A/1 (or successor versions)
• Remote monitoring tools:	CardioMessenger II

• Remote monitoring software:	CardioMessenger II-S
• Holter ECG:	BIOTRONIK Smart 3G (or successors)
	BIOTRONIK Smart 3G AU (or successors)
• Clinical Data Warehouse (platform for acquisition of study-related pseudonymized Home Monitoring data)	HMSC 3 or successors
	Pathfinder®, Spacelabs Heartcare

All devices are used within their intended purpose.

8.1.6 Replacement of subjects

A drop-out rate of 10 % of the total sample size was taken into consideration based on estimates taken from experiences with predecessor devices.

During the course of the study, patients who drop-out prior to any insertion attempt will not be counted in the total sample and will be replaced as long as study enrollment is ongoing.

8.2 Used devices and comparators

8.2.1 Description of exposure to the investigational device

The BIOMONITOR is an Active Implantable Medical Device (AIMD). According to the nature of implantable devices, the investigational device used in this study will be inserted into the patient's body. It may remain in the patients' body until either a diagnosis has been established for the medical issue for which it has been implanted, or until its battery has reached the end of its service time. Even then, it is in the responsibility of the patient and the responsible physician to decide if the device is explanted or remains in the patient's body.

8.2.2 Justification of the choice of comparators

No comparator is used in this study.

8.2.3 List of any other medical device and/or medication to be used during the investigation

Other medical devices used within this study are listed in section 4.3. Further, an external 48-hour holter recorder will be applied. During conduct of the insertion procedure, anesthesia may be used. Additionally, local or systemic antibiotics may be applied to prevent wound infection according to local clinical practice.

No medication is required by this study protocol. However, the medication is at the investigator's discretion according to the medical condition of the patient.

8.2.4 Number of investigational devices to be used and a justification

One BIOMONITOR III per study patient will be used. Additional investigational devices may be used due to device exchange during the study, but this appears unlikely since the nominal lifetime of the device exceeds the study duration.

8.3 Subjects

8.3.1 Description of patient population

Only patients with an indication for ICM system insertion according to current clinical practice and who are planned to be inserted with a BIOMONITOR III according to the investigators' decision may be enrolled in the BIO|MASTER.BIOMONITOR III study. Decision for insertion of the respective BIOTRONIK devices should be based on medical decisions alone and should not

be influenced by the enrollment to this clinical trial. The patient population consists of patients in whom long-term cardiac rhythm monitoring is required for diagnostic purposes. Indications are described in sections 4.1.3 and 4.6.1.

8.3.2 Inclusion criteria

To be eligible for participation in the BIO|MASTER.BIOMONITOR III study, patients must fulfill the following inclusion criteria:

- Patient is at high risk of developing a clinically important cardiac arrhythmia; **or**
 - Patient is undergoing investigation for symptoms such as palpitations, pre-syncope or syncope, that are suggestive of an underlying cardiac arrhythmia; **or**
 - Patient is undergoing investigation for the detection of atrial fibrillation following cryptogenic stroke; **or**
 - Patient is planned for AF ablative procedure or has already undergone an AF ablative procedure.
- Patient is able to understand the nature of the study and to provide written informed consent.
- Patient is willing and able to perform all follow-up visits at the investigation site.
- Patient is willing and able to use the CardioMessenger and accepts the BIOTRONIK Home Monitoring® concept.

8.3.3 Exclusion criteria

The following exclusion criteria shall **not** be fulfilled for enrollment of the patient:

- Patient is implanted with an ICD or pacemaker.
- Patient is pregnant or breast-feeding. Patient is less than 18 years old.
- Patient's life-expectancy is less than 12 months.
- Patient is participating in another interventional clinical investigation according to the definition given below.^{8,9}

Note: The inclusion and exclusion criteria apply at enrollment.

8.3.4 Screening failure

No screening procedure is planned for this study.

8.3.5 Drop-out criteria

Since no invasive, stressful or risky procedures are planned by this protocol after the insertion, it is not allowed that a patient is excluded from the study by decision of the investigator once

⁸ Based on the EU Clinical Trials Regulation a study is considered as interventional which fulfills any of the following conditions: (a) the assignment of the subject to a particular therapeutic strategy is decided in advance and does not fall within normal clinical practice of the Member State concerned; (b) the decision to prescribe the investigational medicinal products is taken together with the decision to include the subject in the clinical study; or (c) diagnostic or monitoring procedures in addition to normal clinical practice are applied to the subjects.

⁹ [REDACTED]

an insertion has been attempted. This does not infringe on the investigators' right, and obligation, to refrain from any study procedure that may not be medically justified. It is merely intended to assure complete reporting of adverse events from the complete study duration.

A drop-out is possible as described in 8.3.5.1 to 8.3.5.6.

8.3.5.1 Patient unable or unwilling to attend required visits

The patient should be prematurely terminated if he or she is permanently unable or unwilling to attend required follow-ups, e.g. if they move away from the investigational site, if they are permanently bed-ridden and have no appropriate transport option, or in comparable cases.

8.3.5.2 Patient is lost to follow-up

The patient should be permanently terminated if he or she is permanently lost to follow-up. In such a case the investigators shall use all justified means to try and contact the patient before premature termination.

8.3.5.3 Patient withdraws consent to study participation

Patients may withdraw their consent for study participation at any time without stating the reason and without any unfavorable consequences. All data which are collected until the date of withdrawal will be used in pseudonymized form as long as their further processing or retention is necessary, e.g. to fulfil a legal obligation. This also applies if the patient has requested data erasure. Depending on the patient's will the collected data will be anonymized then. A withdrawal sheet and a study termination CRF have to be filled in by the investigator.

8.3.5.4 Drop-out according to protocol

The investigator shall exclude a patient due to the following reasons and after all adverse events have been reported and the corresponding eCRFs have been thoroughly completed:

- Patient with no insertion attempt of the BIOMONITOR III within 4 weeks of enrollment
- Patients in whom the insertion fails and no new attempt is planned are terminated after complete reporting of the insertion attempt and all adverse events connected to the failed insertion.
- Patients in whom the BIOMONITOR III was replaced/explanted/deactivated are terminated after complete reporting of the explantation and all adverse events connected to the explantation.

8.3.5.5 Patient death

The investigator shall terminate the patient's study participation after their deaths and report the death as an adverse event on the corresponding eCRF.

8.3.5.6 Enrollment failure

The patients' study participation shall be terminated if, prior to any medical procedure that is required by the study protocol, it is discovered that the patient violates an inclusion criterion or fulfills an exclusion criterion.

8.3.6 Point of enrollment and study termination

The date of enrollment is the date of the informed consent form. Study related procedures, documentation and collection/following of adverse events will start from this time on.

The point of study termination is defined as date of 12-month follow-up for patients with regular study termination.

In case of premature study termination the following rules apply:

- If patients are permanently unable to attend required follow-ups, e.g. if they move away from the investigational site the date of study termination should be the date of last contact of the study team (e.g. investigator or study nurse) with the patient.
- If patient is lost to follow-up, the date of termination shall be the last day, from which the investigator can assume that possible adverse events – had any occurred – would have been reported. In most cases, this would be the date of the last follow-up contact.
- In case of withdrawal of a patient's consent, the date of study termination should be the date of withdrawal of consent.
- If the investigational device could not successfully be inserted, the date of study termination should be the date of the last unsuccessful insertion attempt.
- If the BIOMONITOR III is replaced/explanted/deactivated (e.g. due to subsequent therapies with pacemaker or ICD etc.), the date of termination is the date of explantation.
- In case of patient death, the date of study termination should be the date of death.
- In case the patient terminated prior to study specific procedures because a violation of an inclusion/exclusion criterion was discovered the date when the violation was discovered shall be the date of termination.

Study related procedures and documentation should end at the day of study termination for the respective patient. However, all Serious Adverse Device Effects will be followed for up to 4 weeks after study termination of the respective patient.

8.3.7 Timelines

First patient in (FPI)*:	~ Sep 2019
Last patient in (LPI)*:	~ May 2020
Enrollment period:	~ 9 months
Last patient out (LPO)*:	~ May 2021
Duration of study participation:	~ 12 months
Finalization of study report	~ Aug 2021

The end of the clinical study is defined as the date of study termination of the last patient (Last Patient Out).

* Timelines subject to change without requiring protocol amendments.

9 STUDY PROCEDURES

9.1 Overview

The following study related procedures (Table 3) apply and have to be documented in the respective electronic case report form (eCRF) for each patient enrolled. Subsequent to the enrollment and the insertion of the investigational device, three follow-up visits are scheduled - 1st follow-up after 10 days to 4 weeks after insertion, after 3 months and 12 months after insertion (\pm 14 days). A 48-hour Holter ECG is applied during the 1st follow-up procedure (10 days to 4 weeks after insertion at the latest).

The visits need to take place within a certain time frame as listed in Table 3. However, if circumstances prevent a protocol conform timing of the follow-up, the follow-up shall be performed anyhow and the reason for the protocol violation has to be indicated on a CIP deviation form. If circumstances prevent the presence of the patient at the follow-up visit, the reason for the missed follow-up has to be indicated on the eCRF.

Table 3: Overview of study procedures.

Investigations	Enrollment/Baseline	Insertion	1 st follow-up (10 days to 4 weeks after insertion)	48-hour Holter- ECG	Month 3 (\pm 14 days)	Month 12 (\pm 14 days)
Patient informed consent	x					
Verification of in- and exclusion criteria	x					
Demographics and medical history	x					
Indication for ICM	x					
Medication log	x	x ¹	x ¹		x ¹	x ¹
Insertion of BIOMONITOR III: Information on procedure and assessment of insertion procedure and tool handling		x				
Check of insertion location (wound check)			x		x	
Rating of wearing comfort (after wound healing)			x		x	
Migration of BIOMONITOR III			(x)		(x)	(x)
Explantation of BIOMONITOR III			(x)		(x)	(x)
R-wave measurements (highest and lowest value amplitude)	x	x			x	x
P-wave visibility assessment			x		x	x
Noise burden (%)			x		x	x
Program settings (ProgramConsult and SensingConsult)			x		x	x
Usage of indication-based program sets	x	x			x	x
Program periodic subcutaneous ECG (cycle duration 1 day 'daily')	x					
Program periodic subcutaneous ECG (cycle duration 30 days 'periodic')			x			
Changes in device programming			(x)		(x)	(x)
Device interrogation and electronic data file up-load via ReportShare	x	x			x	x
Apply Holter ECG and read out Holter ECG recordings after 48 hours				x		

Provide CardioMessenger (mandatory) and Remote Assistant III (optional, incl. test of Remote Assistant III)	x				
Activation of Mome Monitoring and registration at the Monitoring Service Center	x				
Usability of Patient App		(x)		(x)	(x)
Documentation on application of imaging techniques (MRI, mammography)		(x)		(x)	(x)
Assessment of programmer performance and programmer software	x	x		x	x
Regular study termination					(x)
Adverse Event and Device Deficiency reporting	x	x	x	x	x
Fill-in eCRFs	x	x	x	x	x

(x)=if applicable

¹In case of an Adverse event

The above mentioned procedures have to be documented in the eCRFs if they are conducted (Table 3). The use of Source Data Sheets is recommended.

9.2 Enrollment and baseline evaluation

Prior to enrollment into the clinical investigation, the investigator has to check whether all inclusion criteria are met and the absence of all exclusion criteria is confirmed. For the enrollment to be valid, the informed consent form has to be signed and dated both by the patient and the investigator. The date of enrollment is defined as the date the patient signed the informed consent. The informed consent process has to be documented in the patient record. After obtaining informed consent, the subject has to be registered in the iMedNet System. After registration, the patient will be assigned a ID code to be used in the study and the patient has to be entered in the patient identification log. The signed informed consent will be verified by sponsor appointed monitoring personnel.

On the enrollment eCRF the following data have to be recorded:

- Version number of the ICF
- Confirmation that the patient met all inclusion and none of the exclusion criteria
- Date of patient signature on the informed consent form
- Date of investigator signature on the informed consent form

After a subject has been enrolled, the following data have to be collected and entered in the Baseline – General, Medical History, and Concomitant Medication Log eCRF, respectively:

- Date of baseline assessment
- Demographic data
- Details on the ICM indication of the patient
- Medical history
- Current concomitant medication

Note: Medication shall be documented in the medication log at baseline and in the context of Adverse events.

9.3 Insertion

The device insertion shall be completed within 4 weeks after informed consent. Otherwise the patient is prematurely excluded from the study and a Termination eCRF has to be filled in. The insertion of the BIOMONITOR III is performed as described in the function manual and in section 4.7.1.10.

The implanting physician determines and documents the device position in accordance with the individual patient characteristics.

During insertion, the handling of the incision and insertion tools will be assessed by the implanting physician. The physician rates the performance as 'excellent', 'good', 'fair', 'poor' or 'very poor'. Furthermore the number of device repositioning has to be documented.

9.3.1 Procedure after device insertion

The following procedures shall be conducted after insertion:

- Interrogate the newly inserted BIOMONITOR III.
- Perform R-wave measurements (see section 9.5.1).
- Program the BIOMONITOR III according to the clinical indication of the patient.
- Use the indication specific program settings (Go to 'Parameters' – 'Program sets' – 'ProgramConsult', Figure 9) if possible.

[figure not shown]

Figure 9: Use 'ProgramConsult' for indication specific programming.

- **Note:** It is strongly recommended that the high pass signal filter is kept at standard value 0.5 Hz.
- Check that the Home Monitoring function is set to 'ON'.
- Store the electronic procedure data (including final device settings, measurements) of the BIOTRONIK programmer. Provide the programmer data by uploading the PDF-File via the ReportShare-function (see 4.7.1.11 and 9.5.4).
- **Note:** Provide CardioMessenger to the patient and register the patient at the Home Monitoring Service Center (HMSC).
- Activate a periodic sECG recording in the 'Patient profile' tab of the HMSC (Go to 'Remote scheduling', press 'edit' and select 'daily'), Figure 10.

[figure not shown]

Figure 10: Activate daily periodic sECG recording in HMSC.

- Explain to the patient how to use the Remote Assistant III correctly and test the functionality of the Remote Assistant III. Let the patient trigger one sECG recording. If the first attempt was not successful, try to find the reason and try again. Check then if an sECG has been finally stored and report on the eCRF.
- If applicable, provide the Remote Assistant III to the patient for further follow-up.
- Answer questions regarding programmer and programmer software handling and document possible problems¹⁰ regarding device programming.
- Enter data in the insertion eCRFs in the iMedNet EDC database. The use of source data sheet is recommended.
- Document any adverse event or device deficiency during the procedure by using the respective eCRF. Please adhere to the reporting timelines listed in section 18.9.

9.4 1st follow-up, 3- and 12-month follow-up

10 days to 4 weeks after insertion (= 1st follow-up), 3 and 12 months (± 14 days) following the insertion, the patient returns to the investigational site for an in-office assessment of his/her BIOMONITOR III. The following procedures shall be conducted:

- Interrogate the BIOMONITOR III.
- Inspect the trend values for the R-wave amplitude (see section 9.5.1) and noise burden (see section 9.5.2) at each regular follow-up visit.
- Adjust patient specific program parameters, if applicable. Use the indication specific program settings (Go to 'Parameters' - 'Program sets' - 'ProgramConsult') if possible.
- **1st follow-up:** Program the periodic subcutaneous ECG recording in the 'Patient profile' tab of the HMSC and change cycle duration to 30 days.
- Store the electronic procedure data (including final device settings, measurements) of the BIOTRONIK programmer. Provide the programmer data by uploading the PDF-File via the ReportShare-function (see 4.7.1.11 and 9.5.4).
- P-wave measurements within the HMSC as described in section 9.5.3.
- **1st and 3-month follow-up:** ask the patient to answer the questions regarding the wearing comfort of the BIOMONITOR III
- **1st and 3-month follow-up:** check of insertion location and device migration (if applicable).

¹⁰ Problem means any deficiency of the programmer or software or any adverse events related to the use of the programmer.

- Ask the patient to answer the questions regarding the usability of the Patient App, if applicable.
- Provide further details in case the patient was diagnosed (concerning the medical indication for the BIOMONITOR III).
- Answer questions regarding programmer and programmer software handling and document possible problems¹¹ regarding device programming.
- Answer questions regarding possible examinations by imaging techniques (MRI, mammography).
- Ensure that all source data from the 1st, 3-month and 12-month follow-up are documented, e.g. using a source data sheet which is recommended, and enter data in the respective eCRFs in the iMedNet EDC database.
- Document any adverse event or device deficiency observed during the follow-up by using the respective eCRF. Please adhere to the reporting timelines listed in section 18.

9.5 Description of measurements and other procedures performed at insertion and follow-up visits

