9.5.3 Assessment of P-wave visibility

The P-wave visibility shall be measured during all follow-up visits (see section 9.4). Assessment of P-wave visibility within the HMSC need to be performed as follows:

1st follow-up

At the day of 1st follow-up, check the first periodic sECG episode that was successfully transmitted to the HMSC. In patients with sinus rhythm, evaluate the number of expected P-waves (i.e. number of complete heart cycles) and P-waves that can undoubtedly be identified.

Check also the latest periodic sECG episode which was successfully transmitted to the HMSC.

In patients with sinus rhythm, evaluate the number of expected P-waves (i.e. number of complete heart cycles) and P-waves that can undoubtedly be identified.

3-month and 12-month follow-up

Check the periodic sECG episode which was successfully transmitted to the HMSC and, which is closest to the 3-month and 12-month follow-up date.

In patients with sinus rhythm, evaluate the number of expected P-waves (i.e. number of complete heart cycles) and P-waves that can undoubtedly be identified.

Enter the dates and values in the follow up SDS. Provide a PDF file export (StatusReport) from the HMSC with the respective episodes and upload the PDF-Files via ReportShare. Alternatively, the PDF files can be sent to the study e-mail address [REDACTED]

In addition an independent core laboratory will compare the P-wave visibility between the 48-hour Holter-ECG device and the sECG from the BIOMONITOR III. For this, the investigational site needs to conduct a 48-hour Holter-ECG and BIOMONOITOR III read out according to section 9.6.

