9.5.4 Data Transfer via Report Share

During the study, programmer data containing all measurements have to be provided to the sponsor for insertion and each follow-up. Furthermore programmer data should be provided also for interim visits of the patient at the study site.

Note: We strongly recommend using Report Share function to facilitate the data transfer to BIOTRONIK.

Automatic export

Pre-setting of Renamic Programmer: open the 'Options' dialog in the Data Manager.

Activate the automatic upload by enabling the 'Automatic export' (3) checkbox (see Figure 13).

After implantation or FU was performed: click 'end' to close the application.

The upload will start automatically.

Or Manual export

Pre-setting of Renamic Programmer: open the 'Options' dialog in the Data Manager.

Activate the manual upload by enabling the 'HMSC export' (2) checkbox (see Figure 13).

Select one follow-up from Data Manager.

Click on 'Preview' and select all checkboxes.

Click on 'Export'.

[figure not shown]

Figure 13: Interface for the export of programmer data to HMSC via ReportShare.

In case that ReportShare is not available, e.g. for organizational or technical reasons, the following alternatives may be used for delivery of programmer data:

- Delivery via email to [REDACTED]
- Delivery via USB flash drive

For every export it has to be ensured that data are pseudonymized.

9.6 48-hour Holter ECG recording

48-hour Holter ECGs are to be recorded from all patients. It is recommended to start recording immediately after the completion of the 1st follow-up.

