9.6.1 Initiation (start day)

1. Preparing the BIOMONITOR III

- Set the clock on the programmer device to the precise local time.
- Delete statistics and episodes ('Recordings' → 'Restart'). This sets the clock of the BIOMONITOR III.

2. Preparing the Holter ECG

- Label flash card with patient ID and date.
- Insert batteries (take a new one for every patient!).
- Insert Flash card.

- Set the clock of the Holter ECG device to the precise local time (via 'Set up' → Time; navigate with yellow button and enter with green button).
- Select 'Start Week' via menu.
- Speech recording (in menu select 'record' and enter with green button).

3. Applying the Holter ECG device

- Attach three ECG electrodes according to Figure 14.

[figure not shown]

Figure 14: Electrode position for Holter ECG.

- Ensure ECG does not alter with change in position/posture.
- Reposition electrodes in case of ECG instability/poor quality.
- Start recording (with green button).
- ECG signal can be displayed by simultaneous pressing of the green and yellow button.
- Use neck lanyard, shoulder pouch or belt clip to attach recorder.

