9.11.3 Responsibilities of the Core laboratory

For the clinical study a core laboratory is contracted for assessment of Holter ECGs. The responsible core laboratory is:

The core laboratory is responsible to identify true arrhythmia episodes in the external Holter ECG.

The corelab will determine the following:

- Arrhythmia detection performance of the sECG

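### Changing the periodic sECG cycle to 30 days just before the 48-hour Holter leaves few scheduled sECGs for the promised core-lab P-wave comparison

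*Protocol*

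**What the plan says.** The relevant steps are spread over several protocol sections.

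- **Section 9.3.1 (after insertion):** a daily periodic sECG is activated by remote scheduling in the Home Monitoring Service Center (HMSC).
- **Section 9.4 (1st follow-up):** "Program the periodic subcutaneous ECG recording in the 'Patient profile' tab of the HMSC and change cycle duration to 30 days". Table 3 in section 9.1 schedules the same change at that visit.
- **Section 9.6 (Holter):** "It is recommended to start recording immediately after the completion of the 1st follow-up". Section 9.1 places both the visit and the Holter between 10 days and 4 weeks after insertion.
- **Section 9.6.1 (Holter start day):** one instruction for preparing the device is "Delete statistics and episodes".
- **Section 9.6.2 (Holter end day):** the recorder is removed, the device is then interrogated, and programmer data including an episode list go to the sponsor.
- **Section 9.5.3:** beyond the investigator's own counts, "an independent core laboratory will compare the P-wave visibility between the 48-hour Holter-ECG device and the sECG from the BIOMONITOR III". The section adds that the site must perform the Holter and the device read-out of section 9.6 for this purpose.
- **Section 8.1.3:** "A periodic sECG was chosen as the sample ECG because during arrhythmia, P-waves are often not present".
- **Section 9.11.3:** the core laboratory identifies true arrhythmia episodes in the Holter, and the only item listed for it to determine is "Arrhythmia detection performance of the sECG". P-wave visibility is not mentioned.

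SAP section 13 analyses P-wave visibility from the investigators' counts of cardiac cycles and P-waves only. It has no variable for a comparison with the Holter.

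**The concern.** The protocol names the periodic sECG as the suitable recording for judging P-waves. It then cuts the frequency of that recording from daily to every 30 days at the visit that precedes the only period in which a reference ECG is worn. Clearing the device memory at Holter start means the later read-out holds only what was recorded from then on. Under the 30-day cycle that is mainly arrhythmia-triggered or patient-triggered material.

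What is at stake is the core-lab comparison. Secondary endpoint 3 is otherwise counted by investigators in an open, single-arm study, and this comparison is the only planned one that sets the device's P-waves against an external reference ECG. Its value depends on having enough suitable sECGs to set against the Holter.

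**Working it through.** **Inputs.** Cycle of 1 day from insertion (9.3.1). Cycle of 30 days from the 1st follow-up (9.4, Table 3). Holter length 2 days (9.6). Planned total 157 patients (11.2). The documents give no expected number of sECGs in the Holter window, so there is no planned count to reproduce. The 157 serves only as a scale, and it does reproduce: 141 / 0.9 = 156.7, rounded up to 157.

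**Formula.** Expected periodic sECGs per patient in the window = 2 days / cycle length in days.

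**Daily cycle kept.** 2 / 1 = 2 per patient, or 2 × 157 = 314 in all.

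**30-day cycle.** The result depends on when the remote change takes effect and when the first recording of the new cycle falls. Neither is stated, so both are assumptions here.

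| Assumption | Per patient | In 157 patients | Loss against daily |
|---|---|---|---|
| Change acts at once, cycle restarts at the change | 0 | 0 | 100% |
| Change acts at once, recording day unrelated to Holter start | 2/30 = 0.067 | 10.5 | 1 − 0.067/2 = 97% |
| One last daily recording still falls in the window | at most about 1 | about 157 | about 50% |

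In the middle row, 1 − 2/30 = 93% of patients would have no periodic sECG during the Holter.

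**Does a later Holter help?** The immediate start is only recommended. Take the earliest visit (day 10) and the latest Holter start (day 28). The Holter ends 28 − 10 + 2 = 20 days after the change, which is before the first recording of a restarted 30-day cycle. Delay within the permitted window therefore does not restore recordings in that case.

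**Other recordings in the window.** Triggered sECGs can show sinus rhythm. Section 4.7.1.5 describes rate-based detection, section 4.7.1 notes that a high-rate detection may be sinus rhythm during exercise, and section 4.7.1.6 has AF termination trigger a recording. For scale, the predecessor study's Holter analysis (5.2.4) reports 318 detected episodes, of which 269 were true, in 82 patients. That leaves 318 − 269 = 49 false detections, or 49 / 82 = 0.6 per patient on average. Not all of these need be sinus rhythm, and they need not be spread evenly over patients. Patient-triggered recordings cannot be counted on, because section 4.7.2 does not require that the patient keep the Remote Assistant.

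**Live sECG at read-out.** Section 9.6.2 interrogates the device after the recorder is off, so that tracing does not overlap the Holter.

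**The case against.** The strongest reply is that section 9.5.3 does not ask for time-matched strips. By the 1st follow-up, 10 days to 4 weeks of daily sECGs have been scheduled for the HMSC. The investigator assesses the first and the latest of them at that visit and exports them as PDF. Nothing says that clearing the device erases HMSC copies. With transmission working, the latest strip precedes an immediately started Holter by about a day, so a near-contemporaneous comparison in the same patient remains possible. This stands in part: that simultaneous recordings are required is an inference. It is a reasonable one, since section 9.5.3 ties the comparison to the section 9.6 read-out, but it is not stated.

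Two stronger readings are tempting and are not supported. A reader might infer that the Holter window will hold almost no sinus-rhythm sECGs. The count above covers scheduled periodic sECGs only; triggered recordings add some sinus rhythm, although they are unplanned and selected. Nor is the 314 a sinus-rhythm count: patients with AF ablation are eligible, and 157 includes the drop-out allowance (at 141 patients the figures are 282 and 9.4). A reader might also infer that secondary endpoint 3 is compromised. It is defined and analysed from investigator counts, has no hypothesis, and does not use the Holter comparison.

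It is also fair to say that moving the switch date alone may not be enough. Section 9.5.3 places periodic sECGs in the HMSC, whereas section 9.6.2 sends programmer data, and the documents do not say whether those data contain periodic sECGs.

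**Conclusion.** The point holds as a scheduling fault affecting an ancillary comparison. As written, the Holter window will contain 0 to 0.07 scheduled periodic sECGs per patient if the change acts at once and at most about 1 if a last daily recording still falls in it, against about 2 under the daily cycle. The size of the loss, about 50% to 100%, rests on device behaviour that the documents leave open, so 97% should not be quoted as the single answer. Earlier daily sECGs in the HMSC permit a comparison, but not a simultaneous one.

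Separately, and whatever the switch delay, section 9.5.3 promises a core-lab task that section 9.11.3 does not list. The primary endpoint, the sample size and all secondary endpoint estimates are unaffected. The change is worth making because it is cheap and makes a promised check workable.

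**What to change.** 1. In section 9.4 and Table 3, move the change from the daily to the 30-day cycle from the 1st follow-up to the Holter end day (section 9.6.2), after the recorder is removed and the device is interrogated. The investigator's P-wave assessment at the 1st follow-up uses sECGs already transmitted, so it does not need the earlier switch.
2. In section 9.6.2, add an HMSC export (StatusReport) of the periodic sECGs recorded during the Holter window, so that they reach the core laboratory.
3. Reconcile section 9.5.3 with section 9.11.3 by listing the P-wave comparison as a core-lab task.

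The cost is a few more daily sECG transmissions and one extra PDF export per patient. The setting is changed remotely and the site already handles the device on the Holter end day, so no visit or staff is added.
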